## **7.4 Baseline-(Visit 2) -Treatment Initiation**

### **7.4.1 Confirmation of Eligibility**

Patients who are deemed eligible in the screening visit will go home to complete a 72-hour voiding diary and return for Visit 2 within 7-14 days after Visit 1. At visit 2, final eligibility will be confirmed by a review of the voiding diary. Subjects eligible to continue will have urinary urgency as evidenced by at least 8 episodes of urgency scores of 2 or greater in 72 hours AND will have urinary frequency as evidenced by having EITHER 8 or more episodes of micturition per 24 hours averaged over 72 hours OR 2 or more episodes of urinary incontinence in 72 hours. In addition to confirming eligibility, the diary scoring will provide the baseline values of mean daily OAB-SCS, number of micturitions per 24 hours, number of incontinence episodes per 24 hours, and mean volume per micturition.

In addition to the diary review, medications will be reviewed again to ensure stability of the PD medication regimen and absence of any prohibited medications. Vital signs will again be measured. At any visit, if a patient is found to have systolic blood pressure over 165, diastolic blood pressure over 100 or heart rate over 100, he or she will be withdrawn from the study.

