### **10.1.2 Vital Signs**

Vital signs (blood pressure, heart rate, and respiratory rate) will be measured at each clinic visit. Subjects with BP > 165 systolic or > 100 diastolic or those with HR > 100 will be excluded at screening or discontinue study medication if this occurs while on study medication. However, they may complete other elements of the study.

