#### 10.1.5 Post-void Residual

PVR will be measured by a bladder scan after urination at Visits 1, 3, and 4. Subjects with PVR > 200 mL will be excluded at screening or will discontinue study medication if this occurs while on study medication. Symptoms of urinary retention will be monitored throughout the study and may lead to early discontinuation of study medication; however, such subjects may complete other elements of the study.

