## 11.4 Safety Analysis

AEs will be summarized by treatment group (study drug or placebo) and by dose. Changes in vital signs (BP, HR, RR) and changes in post-void residual will be analyzed to detect differences between active drug and placebo.

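### Section 11.4 compares arms on changes in BP, HR and PVR, but a subject over a limit at Visit 3 leaves or stops drug, so the Visit 4 change can be diluted; a count of limit crossings by arm is needed.

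*Protocol*

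**What the plan says.** Protocol section 11.4 summarises AEs by treatment group and dose. For the measured safety variables it adds: "Changes in vital signs (BP, HR, RR) and changes in post-void residual will be analyzed to detect differences between active drug and placebo". It names no visit and does not say how withdrawn or off-drug subjects count.

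Three other sections tie continuation to those variables:

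- **BP and HR, section 7.4.1.** The rule applies at any visit, to systolic pressure above 165, diastolic above 100, or "heart rate over 100, he or she will be withdrawn from the study".
- **BP and HR, section 10.1.2.** With the same limits, subjects "discontinue study medication if this occurs while on study medication. However, they may complete other elements of the study".
- **PVR, section 10.1.5.** Subjects above 200 mL "will discontinue study medication if this occurs while on study medication". After the next rule, on symptoms of retention, the section adds that "such subjects may complete other elements of the study".

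Vital signs are taken at each clinic visit and PVR at Visits 1, 3 and 4. The scheduled on-treatment readings are therefore Visit 3 (days 32-40 after Visit 2) and Visit 4 (days 74-82). The dose step takes place at Visit 3. Section 8.3 keeps data collected before discontinuation, and section 11.2 sets an intent-to-treat analysis of all randomised subjects.

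**The concern.** The variable being compared is also the variable that ends treatment. If one arm raises BP, HR or PVR in some subjects, those subjects are the ones most likely to be over a limit at Visit 3. Their later values are then either missing or measured off drug. The Visit 4 mean change loses their contribution, and it does so more in the arm that causes the rise, so the error runs towards no difference.

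Section 11.1 gives safety in this population as a purpose of the trial. Visit 4 is the only scheduled reading after the dose step, so readers will look there for reassurance. The event that the protocol itself treats as unacceptable, crossing a limit, has no dedicated summary by arm.

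**Working it through.** **1. What a Visit 3 crosser contributes**

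| Variable | Governing text | Visit 3 value | Visit 4 value |
|---|---|---|---|
| BP, HR | 7.4.1: withdrawn | kept | none |
| BP, HR | 10.1.2: stops drug, may stay | kept | off drug, if attended |
| PVR | 10.1.5: stops drug | kept | off drug, if attended |

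The gap between the two visits is 74 − 40 = 34 to 82 − 32 = 50 days. No row has an on-drug Visit 4 value.

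**2. Chance that it arises with 20 per arm.** The protocol gives no crossing rate. For an assumed rate p, the chance of at least one crosser in an arm is 1 − (1 − p)^20: 0.64 at 5%, 0.88 at 10%, 0.96 at 15% and 0.99 at 20%.

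**3. Hand example, PVR (assumed).** Two of 20 active subjects rise by 200 mL by Visit 3 and the rest do not change. The mean change at Visit 3 is 2 × 200 / 20 = 20 mL. At Visit 4 it is 0 mL if the two have recovered off drug, and also 0 mL if they are absent. The crossing count remains 2/20 against 0/20.

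**4. Simulation, systolic BP (all inputs assumed).** Values at Visits 2, 3 and 4 are normal with correlation 0.6; entry requires a Visit 2 value of at most 165; a crosser exceeds 165 at Visit 3. There were 400,000 draws per arm before the entry cut. Entries in the last four columns are differences in mean change, active minus placebo, in mmHg.

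| Mean, SD | Drug effect | Crossing at Visit 3, active v placebo | Visit 3 | Visit 4, all on drug | Visit 4, crossers lost | Visit 4, crossers off drug |
|---|---|---|---|---|---|---|
| 130, 15 | +2 in all | 1% v 1% | 2.0 | 2.0 | 2.0 | 2.0 |
| 135, 15 | +3, and +25 more in 10% | 7% v 2% | 5.5 | 5.5 | 4.5 | 4.2 |
| 140, 18 | +3, and +25 more in 10% | 13% v 6% | 5.5 | 5.5 | 4.2 | 3.8 |
| 135, 15 | +3, and +25 more in 20% | 11% v 2% | 8.0 | 8.0 | 6.1 | 5.5 |
| 140, 18 | +5, and +30 more in 20% | 22% v 6% | 11.0 | 11.0 | 7.3 | 5.8 |

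In the rows with a harmed subgroup the loss runs from (5.51 − 4.50) / 5.51 = 18% to (11.02 − 5.81) / 11.02 = 47%. A second set of inputs (mean 138, between-subject SD 14, visit-to-visit SD 9) gives the same picture. With +25 in 20% of active subjects, 5.0 falls to 3.2 (lost) or 2.9 (off drug). With +5 in all, the results are 4.9 and about 4.7.

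**5. Simulation, PVR (all inputs assumed).** Log-normal, median 40 mL, log SD 0.8, correlation 0.5, entry at most 200 mL. With +200 mL in 5%, 10% or 20% of active subjects, true Visit 4 differences of 9.9, 19.8 and 40.2 mL all fall to about 0 under either handling. With +150 mL in 10%, 14.9 mL falls to 9.7 (lost) or 9.3 (off drug). Visit 3 differences are intact throughout.

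**6. Last on-treatment value as a check.** Using the Visit 3 reading for crossers gives 5.9 to 11.8 mmHg against true 5.5 to 11.0, and 9.9 to 39.6 mL against 9.9 to 40.2. It slightly overstates systolic BP, because readings selected for being high are retained.

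**7. Scale against noise.** With a visit-to-visit SD of 9, the SD of a change is 9√2 = 12.7, and the standard error of the difference with 20 per arm is 12.7 × √(2/20) = 4.0 mmHg. A loss of 1.8 mmHg (5.0 to 3.2) or 2.1 mmHg (5.0 to 2.9) is about half a standard error.

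**The case against.** Much of the case on the other side stands.

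- **The harm is not removed from the analysis.** A reader might infer that harmed subjects vanish. They do not: the Visit 3 crossing value is kept under 8.3 and 11.2, and section 11.5 lists Visit 3 among the time points for comparative measures. Section 11.4 does not confine itself to Visit 4. The problem is limited to the Visit 4 change.
- **No 50 mg reading is lost.** A reader might also infer that harm at the higher dose is hidden. A Visit 3 crosser was on 25 mg or placebo and stops there, so a 50 mg value never exists. A crossing first seen at Visit 4 is captured. Only subjects without an AE step up (7.5.1, 9.2), so Visit 4 is not a clean 50 mg comparison in any case.
- **Crossings can be reported as AEs.** The synopsis lists PVR as a screen for retention as an AE, section 10.1.6 includes markedly abnormal test results, and 11.4 summarises AEs by arm. This route depends on the investigator's judgement, so it does not guarantee a complete count.
- **Withdrawal in 7.4.1 covers BP and HR only.** For PVR the stated consequence is stopping drug. An absent Visit 4 value would need another cause, such as discretionary withdrawal under 8.3.
- **An off-drug reading is legitimate under intent-to-treat.** It is a valid value for that comparison, but it does not describe values on drug.
- **Threshold tables usually belong in the SAP, which is not at hand.** Their absence alone would be no finding. The point rests on how the protocol's own comparison and its own stopping rules interact, and on two sections that disagree.

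**Conclusion.** The point holds as a limited one. The Visit 4 comparison of changes in BP, HR and PVR contains no on-drug value from anyone who crossed at Visit 3, and it is diluted towards no difference when a minority has a large rise. Under the assumed inputs, the loss for systolic BP is 18% to 47% with a harmed subgroup and negligible for a uniform shift. For PVR it can be nearly complete when the rise itself carries subjects over the limit. Every size rests on distributions and crossing rates that the protocol does not supply; if crossings are rare, the effect may be negligible.

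The documents do not support a claim that the safety analysis as a whole misses the harm. What remains is a cheap improvement to 11.4 and a contradiction to settle: 7.4.1 and 10.1.2 disagree on whether a subject over a BP or HR limit leaves the study, and that decides whether Visit 4 values are missing or off drug.

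**What to change.** 1. In 11.4, add by arm, for all randomised subjects (including any later replaced), the number and proportion crossing each protocol limit (systolic, diastolic, HR, PVR) at any post-baseline on-treatment assessment. Show scheduled visits alone as well, because unscheduled readings may not be equally frequent in both arms.
2. Report Visit 3 and Visit 4 changes separately. Keep off-drug Visit 4 readings in the intent-to-treat comparison, identify them, and state the number missing.
3. Give the change to the last or highest on-treatment value only as a supportive summary. State that it is noisier, and that it rests on one scheduled reading for Visit 3 stoppers and two for completers.
4. Reconcile 7.4.1 with 10.1.2. This point takes no view on which rule, or which limit, is right.

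The cost is a few sentences and one small table, with no new measurements. The count should be read descriptively: 2/20 against 0/20 has a two-sided Fisher p of 2 × C(20,2)/C(40,2) = 2 × 190/780 = 0.49. Its value is that the stopping rule cannot dilute it.

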## 11.5 Efficacy Analysis

Outcome measures are described in section 10.2. Analysis of primary and secondary outcome measures will include:

- Summary statistics (n, mean, standard deviation, median, minimum and maximum) at baseline, visit 3 and visit 4 by treatment.
- Summary of % change from baseline to visit 3 and 4.
- Significance testing

The primary time points for all comparative measures will be Baseline Visit (Visit 2), Titration Visit (Visit 3) and Final Visit (Visit 4). Outcome measures will be compared between groups using analysis of covariance (ANCOVA) or other method as deemed appropriate by the consulting statistician. Demonstration of superiority will depend on achieving statistical significance for the primary endpoint. Level of significance will be defined as  $p = 0.05$ . All statistical tests will be two-sided.

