### **8.3 Removal of Patients from Study**

A patient will be considered to have completed the study when he or she has completed all study visits through the final visit. Every patient has the right to discontinue study participation at any time at his/her own request, or may be withdrawn at any time at the discretion of the investigator for safety, behavioral, or administrative reasons. Criteria for early termination include, but are not limited to, < 36 hours of time covered in a bladder diary, poor adherence to study medication (less than 70% of study medication consumed), loss of health insurance coverage, and safety issues related to study-related or non-study related adverse events.

If a patient has a clinical necessity to alter their standard PD medications, the patient will be withdrawn from the trial so that changes may be made, except that occasional additional doses of carbidopa/levodopa will be allowed if needed to address periodic worsening of parkinsonian symptoms. Additional doses of carbidopa/levodopa taken during the 72-hour diary periods will be recorded in the diary. If a patient is withdrawn due to an adverse event, the event will be followed, when possible, until resolution. Patients who withdraw from the study may be replaced, but withdrawn patients will not be re-entered into the study.

All data generated up to the time of discontinuation from the study will be analyzed and the reason(s) for discontinuation will be recorded.

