## **10.2 Efficacy Assessments**

### **10.2.1 OAB-SCS**

The primary outcome measure will be the change in the mean daily Overactive Bladder-Symptom Composite Score (OAB-SCS) from baseline to visit 4. . One of the secondary outcome measures will be the change in the mean daily OAB-SCS from baseline to visit 3. The OAB-SCS requires subjects to record the severity of urgency of each micturition over a 72-hour period as follows: 1 = no urgency (normal voiding); 2 = mild (could postpone voiding for as long as necessary without fear of incontinence); 3 = moderate (could postpone voiding for a short while without fear of leakage); 4= severe (could not postpone, had to rush to the toilet); 5= urgency incontinence (could not make it to the toilet without some leakage). The total score is derived by adding the urgency rating of each micturition over a 72-hour period as recorded in a voiding diary. In this way, the OAB-SCS accounts for both frequency and urgency in OAB, and is therefore a more accurate assessment of OAB than measurements of urgency alone (Starkman 2008). Mean daily OAB-SCS is total 72-hour score divided by 3. For incomplete days, the daily score will be adjusted to equal [(total score for the incomplete day / actual number of hours recorded) x 24 hours] (Zinner 2005).

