## 11.2 Study Population

The study population will include all patients who pass screening and undergo randomization. Data will be analyzed in an intent-to-treat fashion.

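### ANCOVA of change to Visit 4, if run without imputation, leaves out subjects with no Visit 4 diary and fits poorly with the all-randomised ITT set; a model of Visits 3 and 4 fits better

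*Protocol*

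**What the plan says.** Section 10.2.1 fixes a single-time-point endpoint: "The primary outcome measure will be the change in the mean daily Overactive Bladder-Symptom Composite Score (OAB-SCS) from baseline to visit 4". Section 11.5 gives the method: "Outcome measures will be compared between groups using analysis of covariance (ANCOVA) or other method as deemed appropriate by the consulting statistician". It makes superiority depend on the primary endpoint, tested two-sided at 0.05.

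Section 11.2 defines who is analysed: "The study population will include all patients who pass screening and undergo randomization", and "Data will be analyzed in an intent-to-treat fashion". Section 8.3 adds that "All data generated up to the time of discontinuation from the study will be analyzed".

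The same score is also measured mid-study: "One of the secondary outcome measures will be the change in the mean daily OAB-SCS from baseline to visit 3" (10.2.1). The Visit 3 diary is reviewed at that visit, 32-40 days after baseline (7.5.1).

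There are several ways out after randomisation. Section 8.3 begins its list "Criteria for early termination include, but are not limited to, < 36 hours of time covered in a bladder diary" and goes on to adherence under 70%, loss of insurance and safety. It separately withdraws subjects who need a change of PD medication. On the blood pressure and heart rate limits, 7.4.1 says of a subject who exceeds them at any visit that "he or she will be withdrawn from the study". Section 10.1.2 says that such a subject stops study drug but may complete the rest of the study.

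The only visible rule for missing diary data pro-rates incomplete days (10.2.1). It does not cover a diary that is absent altogether.

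**The concern.** A subject who leaves between Visit 3 and Visit 4 has a baseline score and a Visit 3 score but no Visit 4 score. An ANCOVA of Visit 4 change without imputation has no outcome for that subject, so the deciding test becomes a comparison of completers. Several exits can come to light at Visit 3 itself, when vital signs are taken, returned medication is counted and the Visit 3 diary is in hand.

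If those who leave differ in their Visit 3 score, and differ by arm, the completer comparison is biased. With 20 per arm, three or four such subjects matter. The Synopsis expects any effect found here to inform the size of a larger study, so a biased estimate would carry forward.

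**Working it through.** **The plan's own figure.** Section 11.1 justifies 40 subjects (20 per arm) by an evidence-class convention. It gives no effect size, SD, power or dropout rate, so there is nothing to reproduce. For scale, the effect detectable with 80% power is (1.960 + 0.842) × √(2/n):
- n = 20 per arm: 2.802 × 0.316 = 0.886 SD
- n = 16 per arm (20% without Visit 4 data): 2.802 × 0.354 = 0.991 SD

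**The two estimators.**
- Completer ANCOVA: regress the Visit 4 score on arm and baseline in subjects with a Visit 4 diary. The arm coefficient is the estimate.
- Two-visit likelihood: regress the Visit 3 score on arm and baseline in all with a Visit 3 diary (arm effect τ₃). Regress the Visit 4 score on arm, baseline and Visit 3 score in those with both (arm coefficient θ, Visit 3 coefficient γ). The Visit 4 effect is θ + γτ₃. With this pattern of dropout it is equivalent to a repeated-measures model with unstructured covariance.

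Loss rates, correlations, dropout mechanisms and effect sizes below are assumptions; the protocol gives none.

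**Check 1: no true effect, score-related loss in the active arm.** There are 20 per arm. The dropout probability after Visit 3 is 0.20-0.25 on active at an average score and 0.10 on placebo. The log-odds rise by 1.0-1.5 per SD of the Visit 3 score on active, giving 17-21% loss overall.
- Completer ANCOVA: bias 0.05-0.19 SD in favour of active for correlations of 0.5-0.8; two-sided type I error about 5-10%.
- With all three visits equally correlated at 0.5-0.7, one run gave the low end: bias 0.04-0.09 SD, type I error 5.1-6.2%.
- Two-visit likelihood: bias within about 0.01 SD of zero.

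As a rough guide to what this means for the test, a bias of 0.16 SD with a standard error of 0.31 SD is a shift of 0.16/0.31 = 0.52 standard errors. The rejection rate is then P(Z > 1.44) + P(Z < −2.48) ≈ 0.075 + 0.007, or about 8%.

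**Check 2: true effect 0.80 SD at Visit 4, score-related loss in the placebo arm.** The true effect at Visit 3 is 0.50 SD, and loss on active is random at the same rate.

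| Loss | Visit 3-4 correlation | ANCOVA estimate | Two-visit estimate | Power, ANCOVA | Power, two-visit |
|---|---|---|---|---|---|
| 10% | 0.5 | 0.75 | 0.81 | 58% | 64% |
| 10% | 0.7 | 0.72 | 0.79 | 55% | 63% |
| 20% | 0.5 | 0.70 | 0.80 | 47% | 58% |
| 20% | 0.7 | 0.66 | 0.80 | 43% | 61% |

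Here the completer analysis understates the drug effect. The direction depends on which arm loses its poor responders.

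**Check 3: random loss.** Neither method is biased. At 15% loss the standard error fell from 0.285 to 0.279 (2.1%), 0.309 to 0.300 (2.9%) and 0.292 to 0.279 (4.5%) in three settings. At 20% loss it fell from 0.356 to 0.349 (2.0%, correlation 0.5) and from 0.364 to 0.346 (4.9%, correlation 0.7). Across 10-30% loss, power rose by about 1-6 points.

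**Check 4: half of the leavers also lack a Visit 3 diary.** At 20% random loss the two-visit model uses about 36 of 40 subjects, against 32 for ANCOVA, and power moves from 57% to 58%.

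**The case against.** The strongest reply is that nothing is fixed wrongly. Section 11.5 lets the statistician choose another method, so the two-visit model is already allowed. A missing-data rule may stand in an analysis plan that is not shown. A reader might infer that the protocol commits to dropping subjects without a Visit 4 diary. It does not say so, and ANCOVA after imputation would keep them. This reply stands and limits the point to a poor fit between the only named method and the stated analysis set. It does not remove the point: permission is not commitment, and the clause leaves the deciding test to be chosen later.

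A reader might also infer that 8.3 is contradicted outright. It is not. A leaver's Visit 3 diary enters the Visit 3 summaries and the secondary comparison. What is lost is its use in the primary test.

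A third tempting reading is that the completer analysis favours mirabegron. The documents do not support a direction. They list no exit for lack of efficacy, and adherence or voluntary withdrawal tracking response is an assumption. Check 2 gives the opposite sign from Check 1.

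Finally, the two-visit model does not fully restore intent-to-treat. Subjects with no on-treatment diary add nothing to the contrast. The model predicts leavers from subjects who continued, many of them after the Visit 3 up-titration. Some subjects who stop drug may still provide a Visit 4 diary under 10.1.2 and 10.1.5, which would reduce the problem at source.

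**Conclusion.** The point holds as a should-fix matter, with medium confidence. The named default, run without imputation, gives a completer comparison for the endpoint that decides superiority, while 11.2 and 8.3 lead the reader to expect more.

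The consequence is conditional. Bias is about 0.05-0.19 SD, in either direction, if loss after Visit 3 is 17-21%, depends on the Visit 3 score and differs by arm. It is zero if loss is random, and the precision gain is then only about 1-5% of the standard error at 15-20% loss. The case for the two-visit model is protection against bias, not power.

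**What to change.** In 11.5, replace the open method clause with a named primary analysis: a repeated-measures model of mean daily OAB-SCS at Visits 3 and 4. Include arm, visit, arm-by-visit, baseline and baseline-by-visit, with unstructured covariance and small-sample degrees of freedom. The Visit 4 arm contrast is primary. The arm-by-visit term is needed because Visit 3 precedes the dose increase. The same model supplies the Visit 3 secondary comparison. Keep completer ANCOVA as a sensitivity analysis.

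State the limits beside it: missing at random is assumed given baseline and Visit 3; leavers are predicted from those who continued, many after up-titration; and subjects with neither on-treatment diary are not recovered.

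Reconcile 7.4.1 with 10.1.2 on whether subjects over the vital-sign limits leave the study or may complete it, because this helps determine how many Visit 4 diaries are missing.

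The analysis change costs wording only; every score it needs is already collected.
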